Registration: Once a potential donor has been identified for respective patient, both the patient / recipient and the relative/ donor will sign consent to participate in the study. Upon signing the consent, donor will undergo protocol mandated screening for eligibility. Once donor's eligibility is confirmed both patient and donors will be registered for the study by OHRS research staff.

Each participant will be given a unique identifier code. No patient will start treatment prior to registration.

All eligible patients will be treated at [REDACTED] and receive standard treatment per Blood & Marrow Transplant Program Policies.

1. Patients in cohort 1 will be treated initially with IAC within 42 days after hematopoietic engraftment (both neutrophils and platelets). Engraftment is

defined by 3 consecutive measurements with absolute neutrophil count > 500/mm³ and platelets > 20,000/mm³ without transfusion.

2. Patients in cohort 2 with *high-risk* disease will be treated initially with IAC within 120 days after hematopoietic engraftment (neutrophils and platelets). Chimerism studies must reveal engraftment of donor CD3+ cells > 80% and there must not be any evidence of > grade I *acute* GVHD or *severe* chronic GVHD, per standard CIBMTR staging.
3. Patients in cohort 2 being treated for *relapsed* disease may receive initial treatment with irradiated allogeneic cells any time after relapse documented. They may receive disease specific therapy prior to the experimental cell therapy, but they must have recovered from the disease-specific therapy prior to the experimental cell therapy.
4. All treated patients who do not have evidence of relapse or progressive disease may be treated q 8-12 weeks for up to 3 treatments with delays up to 8 weeks as clinically indicated.
5. Donor will undergo evaluation at RWJ Blood Services within 7 days of each infusion.
6. Donors meeting eligibility requirements will be harvested by leukapheresis with targeted CD3+ (0.5-3.0 x 10⁸/kg); harvesting will be done according to FACT and AABB guidelines.
7. Donor cells (0.5-3 x 10⁸ CD3+/kg) will be irradiated (25 Gy) and infused no more than 24 hours after harvesting of the cells; in case of ABO incompatibility either RBC depletion will be undertaken or the product will be split to assure infusion of \leq 10 ml ABO incompatible RBC/day.
8. Management of cytopenias, infections, and other complications will conform to standard procedures at the discretion of the physician.

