9. Disease status: Disease status will be evaluated every 8 weeks by history, physical examination, laboratory studies and bone marrow aspirate and biopsy as indicated by disease state and clinical parameters.
10. Rh- recipients of child bearing potential who are anticipated to receive a Rh+ product will receive Rhogam at standard dose.
11. Anti-coagulant treatment of any form (Heparin/ Warfarin/ Apixaban etc. will be withheld for one day prior to harvesting of cells from the donor
12. IAC products will meet preparation and release criteria as outlined below:
 - a. Donor leukapheresis volume will be 2.5-3.0 blood volumes or as determined by blood services.
 - b. The leukapheresis product will be appropriately labeled with: 2 patient-specific identifiers, the name of the product, the product unit number, the expiration date, donor Rh/ABO type, and the statement: "Caution: New Drug – Limited By Federal Law To Investigational Use Only".
 - c. If there is a major ABO incompatibility, the product will either be split so that no more than 10 ml ABO incompatible RBC be infused/day or undergo RBC depletion to \leq 10 ml of RBC.
 - d. The product will be transported to the [REDACTED] Hospital Transfusion Services where it will undergo irradiation (25 Gy)

according to standard operating procedures. A label indicating irradiation will be attached.

e. The product will then be assigned to the patient and the released product will be transported to and administered to the patient at [REDACTED] after pre-medication of the patient with acetaminophen 650 mg PO and diphenhydramine-HCl 25 mg PO.

d) Preliminary Data

See the research significance section above and references. IAC is an effective therapy for selected patients with renal cell carcinoma. Individual responses have also been seen in AML and CML (6, [name] personal observation). There is also evidence that allogeneic cells can induce a host CD8+ T cell response directed an AML-associated epitope (7).

e) Sample Size Justification/Statistical Analysis

The primary aim of this pilot study is to see if there is acceptable tolerance (no irreversible grade 3 or higher) experimental treatment-related serious adverse effects and any disease response for 10 patients in each cohort. This will ensure that there is at least an 80% chance that the true unacceptable rate is less than 30%. The study will be closed if there is >1 irreversible grade 3 or higher experimental treatment related adverse effect in either cohort.

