If there is (1) a steroid refractory GVHD or (2) graft failure in cohort 2, then the study will stop.

The secondary aim is to determine if there is evidence of disease response to IAC. If there is evidence of disease response in either arm, additional studies will be planned.

f) Study Variables

• *Independent Variables or Interventions*

IAC infusion every 8-12 weeks as tolerated and feasible.

Toxicity will be measured by occurrence of any experimental treatment-related Adverse Events (AE) up to 12 weeks of completion of therapy. The CTCAE Version 4.0 will be utilized for the description and grading of the AE. All symptoms, signs, or diseases assessed as experimental treatment-related will be captured and graded by a study investigator and an attribution will be associated to the experimental therapy (IAC).

Attribution of the AE:

- Definite – The AE is clearly related to the experimental therapy
- Probable – The AE is likely related to the experimental therapy
- Possible – The AE may be related to the study treatment
- Unlikely – The AE is doubtfully related to the study treatment
- Unrelated – The AE is clearly NOT related to the study treatment

Any experimental treatment-related irreversible grade 3 or higher AE (definite, probable or possible) will result in that patient not receiving any further treatment. If the AE corrects completely or to Grade 1 within 2 weeks, repeat treatment as directed by protocol may be utilized. If there is more than one such irreversible experimental treatment-related Grade 3 adverse event, the study will be terminated for that cohort.

Since a major concern is that the IAC might trigger an immune response that results in steroid-refractory GVHD OR graft failure (in cohort 2), specific parameters to diminish the likelihood of these events are included in the inclusion criteria (e.g. durable engraftment and high donor chimerism). Furthermore, the study will be terminated if even a single episode of these events occurs.

Overall response rate will be defined as the proportion of patients meeting the criteria for partial response (PR), very good partial response (VGPR) and complete response (CR). Disease response will be determined by Standards of Blood and Marrow Transplant Program disease-specific parameters.

- *Dependent Variables or Outcome Measures*

Toxicity and disease response will be measured. Disease response will use standard disease-specific parameters.

g) Drugs/Devices/Biologics

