- Patients undergoing haploidentical allogeneic hematopoietic stem cell transplants are not eligible; patients undergoing < 10/10 HLA allele matched allogeneic transplant are not eligible
- Pregnant women
- Children are not eligible as the transplant program is certified as an adult only transplant program.

(5) Subject Screening - DONOR

(a) Inclusion Criteria - DONOR

- Donor must be related to patient and be partially ($\geq 3/6$ antigen) HLA-matched.
- Donor must meet all RWJ Blood Services requirements for hematopoietic stem cell donation including:
 - Age ≥ 18 years old;
 - normal hemogram (WBC $4.0-10.0 \times 10^3/\text{mm}^3$; platelet count 150,000 to $440,000/\text{mm}^3$; Hemoglobin/Hematocrit; 12.5-18 g/dl, 38 to 54%)
 - not pregnant or lactating;
 - not HIV-1, HIV-2, HCV, Hepatitis B core or HTLV-I/II seropositive; HB S ag (-); meet other infectious disease screening criteria utilized by RWJ Blood Services;
 - no uncontrolled infections, other medical or psychological/social conditions, or medications that might increase the likelihood of patient or donor adverse effects or poor outcomes;
 - meet other blood bank criteria for blood product donation (as determined by RWJ Blood Center screening history and laboratory studies).
- Male and female and all ethnic groups are eligible provided they are fluent in English.

(b) Exclusion Criteria

- Non-English speaking person
- Pregnant women
- Children are not eligible as the transplant program is certified as an adult only transplant program.

(6) Recruitment Materials

N/A

(7) Lead Site Recruitment Methods

N/A

- **Subject Randomization**

N/A

- **Secondary Subjects**

N/A

- **Number of Subjects**

- (1) Total Number of Subjects**

A total of 20 subjects will complete the study. There will be 10 patients in each cohort. There will be a donor corresponding to each patient. There may be additional potential; donors screened if a donor fails the screening.

- (2) Total Number of Subjects If Multicenter Study**

N/A

- (3) Require Number of Subjects to Complete Research**

The number of subjects needed to complete the research procedures (i.e., numbers of subjects excluding screen failures.) is 40 (twenty patients and twenty donors). Each patient will participate in the study for 3 infusions and then be followed until disease progression or 3 years. Patients will be enrolled over a 3 year period of time.

- (4) Feasibility Of Recruiting**

We expect to enroll 7 subjects per year onto this study.

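### The response rule does not say how to count a response that follows other anti-tumour therapy, so such a response would be credited to IAC

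*Combined protocol and SAP*

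**What the plan says.** **Background treatment.** The Treatment Plan (section c, under Registration) says that all eligible patients "receive standard treatment per Blood & Marrow Transplant Program Policies". The content of those policies is not given.

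**Therapy before IAC.** Item 3 of the Treatment Plan is the only rule on the order of treatments, and it covers only cohort 2 patients treated for relapse: "They may receive disease specific therapy prior to the experimental cell therapy, but they must have recovered from the disease-specific therapy". It states no interval.

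**Therapy during IAC.** The patient inclusion and exclusion lists, Treatment Plan items 1 to 12, the Schedule of Events and the criteria for removing a subject do not mention other anti-tumour therapy during the IAC course, donor lymphocyte infusion between infusions, or withdrawal of immunosuppression. The schedule has no entry for concomitant therapy.

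**Response.** Section f begins "Overall response rate will be defined as the proportion of patients meeting the criteria for partial response (PR), very good partial response (VGPR" and adds complete response. It sets no baseline and no condition on other treatment.

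**Decision.** Section e asks about response to IAC and says: "If there is evidence of disease response in either arm, additional studies will be planned". The same section puts "any disease response for 10 patients in each cohort" into the primary aim, and the overview lists disease response under Primary Endpoint(s).

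**The concern.** Section e asks a causal question, response to IAC, in a study without a control group. The answer depends on which responses are counted, and the definition counts them all. A patient who improves after another anti-tumour treatment is recorded in the same way as one who improves after IAC alone.

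The plan sees this problem for harm but not for benefit. The risk section (Other Foreseeable Risks) admits that effects of disease, transplant therapy and IAC on toxicity may be hard to tell apart, and section f gives a five-level attribution scale for adverse events. Response has no counterpart.

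At stake is the study's main output. Section c says that the study is meant to show whether IAC should be developed further. A response produced by another treatment could support that decision, and a reader of the results could not detect it, because the other treatment is not a recorded study item.

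**Working it through.** **1. The plan's own figure.** Section e claims "at least an 80% chance that the true unacceptable rate is less than 30" percent. With n = 10 per cohort ("There will be 10 patients in each cohort") and a limit of one event ("The study will be closed if there is >1 irreversible grade 3 or higher experimental treatment related adverse effect in either cohort"):

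- One event: P(X ≤ 1 | 0.30) = 0.7^10 + 10 × 0.3 × 0.7^9 = 0.0282 + 0.1211 = 0.1493, so the confidence is 1 − 0.1493 = 85.1%. The one-sided 80% upper bound is 27.1%.
- No event: 1 − 0.0282 = 97.2%, upper bound 14.9%.

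The statement reproduces as a one-sided confidence statement. It concerns toxicity only. The response rule has no stated threshold and no error rate.

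**2. Following a confounded response through the plan.** Take a patient with measurable disease who receives another anti-tumour agent during the IAC course and then reaches a partial response.

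- *Entry:* no eligibility criterion addresses other therapy during IAC.
- *Baseline:* the schedule puts staging at screening, within 14 days of registration, and registration is within 7 days of the planned first treatment. Staging is therefore at most about 14 + 7 = 21 days before the first infusion. A footnote makes it subject to clinical indication. Neither item 3 nor section f requires that it follow pre-IAC therapy or serve as the baseline.
- *Course:* infusions are 8 to 12 weeks apart with delays of up to 8 weeks. If the delay may apply to each interval, the third infusion comes 2 × 8 = 16 to 2 × (12 + 8) = 40 weeks after the first. Follow-up runs to progression or 3 years.
- *Counting:* section f counts the response.
- *Decision:* section e treats it as evidence of response.

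No step stops it or marks it.

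**3. Illustration of size.** The documents give neither the response rate from other therapy (q) nor the number of patients per cohort who are both evaluable and exposed to it (m). Both are assumptions. So is reading the decision rule as at least one responder. With IAC inactive and patients independent:

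- one cohort: 1 − (1 − q)^m
- either cohort: 1 − (1 − q)^(2m)

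| m of 10 | q | One cohort | Either cohort |
|---|---|---|---|
| 3 | 5% | 14.3% | 26.5% |
| 3 | 10% | 1 − 0.9^3 = 27.1% | 1 − 0.9^6 = 46.9% |
| 3 | 20% | 48.8% | 73.8% |
| 3 | 30% | 65.7% | 88.2% |
| 2 | 10% | 19.0% | 34.4% |
| 5 | 10% | 41.0% | 65.1% |
| 10 | 10% | 1 − 0.9^10 = 65.1% | 1 − 0.9^20 = 87.8% |

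If nobody is exposed (m = 0), this route adds nothing. The row with m = 10 is an upper case for q = 10%, because cohort 2 includes patients treated prophylactically. A patient already in complete remission without measurable residual disease cannot show a new response.

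**The case against.** The strongest reply is that the plan never says anti-tumour treatment is given alongside IAC. A reader might infer from the standard-treatment sentence that every patient receives it. The documents do not support that: section c lists transfusions, infection prophylaxis, nutrition and isolation, and the risk section explains standard treatment as transplant therapy. This part of the reply stands. The defect is an omission, not a stated practice.

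There is also partial protection:

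- The overview admits relapsed cohort 2 patients only when standard donor lymphocyte infusion or other standard therapy is not an option. This is an entry condition for one subgroup and is not repeated in the inclusion list. It should be reconciled with item 3, which allows disease-specific therapy before IAC.
- Item 4 limits infusions to patients without relapse or progression, a subject whose condition worsens is removed, and follow-up ends at progression. Much salvage treatment would therefore fall outside the IAC course. An agent added during stable or persistent disease, or treatment to deepen a response after transplant, would not.
- The tumor study group may assess response by clinical analysis and reviews patients weekly, so it could discount a confounded response. Nothing instructs it to.
- Treatment dates may be in the medical record or the transplant registry forms that the plan draws on. The plan does not name them as study data.

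A reader might also infer that a single response automatically commits the sponsor to another study. Section e speaks only of evidence of response and gives no number, so the one-responder trigger is an interpretation. Finally, this is a 20-patient tolerance pilot and the consequence is the planning of more research. That limits the harm, but the planning decision still has to be interpretable.

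**Conclusion.** The concern holds in a limited form. The plan neither excludes nor records other anti-tumour therapy during the IAC course and has no rule for discounting its effect, and it allows such therapy before IAC in relapsed cohort 2 patients without tying response to a later baseline. Applied as written, the response definition would credit IAC with a response produced by another treatment.

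The size cannot be derived from the documents. With 3 of 10 patients per cohort evaluable and exposed, q = 10%, inactive IAC and one responder as the trigger, the false-signal chance is 27% per cohort and 47% in either. The corresponding 65% and 88% require all patients to be evaluable and exposed, and should not be read as expected values. The toxicity justification is unaffected.

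This should be corrected before response is used for a development decision. It does not invalidate the safety aim.

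**What to change.** Add to section f, in words such as:

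> Response is measured from disease staging done after any pre-IAC disease-specific therapy and before the first infusion. A response counts toward IAC only if no other anti-neoplastic therapy or donor lymphocyte infusion was given between that staging and the response. All other responses, including those during withdrawal of immunosuppression, are listed separately and do not by themselves lead to further studies.

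At the existing screening, pre-cycle and 30-day visits, record these treatments with dates, including the last date of any pre-IAC therapy. Reconcile the overview's entry condition for relapsed patients with item 3.

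The cost is a paragraph in section f, one data entry at visits already scheduled, and a firm requirement for the screening staging where it is now subject to clinical indication. The downside is that fewer responses will count toward IAC; if other therapy turns out to be common, that loss could be substantial. The rule also cannot remove a late effect of the transplant or of therapy given before staging, although the recorded dates let a reader judge that. No change to what patients may receive is proposed.

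### For prophylactic Cohort 2 patients, the GVHD and donor-chimerism limits are set for the first infusion but are not clearly carried forward to infusions 2 and 3

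*Combined protocol and SAP*

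**What the plan says.** All references are to the combined protocol and SAP.

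- **First infusion.** Treatment Plan item 2 opens: "Patients in cohort 2 with *high-risk* disease will be treated initially with IAC within 120 days after hematopoietic engraftment (neutrophils and platelets"). It continues: "Chimerism studies must reveal engraftment of donor CD3+ cells > 80% and there must not be any evidence of > grade I *acute* GVHD". The same sentence also rules out severe chronic GVHD and names CIBMTR staging.
- **Later infusions.** Item 4 reads: "All treated patients who do not have evidence of relapse or progressive disease may be treated q 8-12 weeks for up to 3 treatments". It names no GVHD grade and no chimerism level. Its only allowance on timing is "with delays up to 8 weeks as clinically indicated". Section f) Study Variables describes the schedule as "IAC infusion every 8-12 weeks as tolerated and feasible".
- **Adverse event (AE) rule, section f).** "Any experimental treatment-related irreversible grade 3 or higher AE (definite, probable or possible) will result in that patient not receiving any further treatment". Repeat treatment is allowed if the event resolves, or falls to grade 1, within two weeks. Grading is by CTCAE version 4.0.
- **Study stop, sections e) and f).** A single steroid-refractory GVHD or graft failure in Cohort 2 ends the study. No attribution condition is attached.
- **Where the safeguards are said to be.** Section f) places the parameters meant to make those two events less likely in the inclusion criteria. The patient inclusion and exclusion lists give no GVHD grade and no chimerism percentage, so item 2 is the only visible source.
- **Schedule of events.** The pre-cycle column lists history, examination and toxicity assessment within 7 days before each infusion. It lists neither GVHD staging nor chimerism.

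**The concern.** The protocol treats GVHD and loss of the graft as its main hazard in Cohort 2. It uses preset limits to reduce that hazard and closes the study at one severe episode. Yet the limits are written for the first of up to three infusions. A patient whose condition would have failed item 2 can reach infusion 2 or 3 under a rule that asks only about relapse and progression.

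The study stop acts after the harm it is meant to catch. The patient-level AE rule depends on severity and on attribution to IAC. The section on other foreseeable risks concedes that toxicity from the disease, the transplant and IAC may be hard to tell apart. A condition based on GVHD stage would apply whatever the attribution. Without one, two investigators could treat the same patient differently and both be following the text.

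**Working it through.** **1. The plan's own figure.** Section e) claims that 10 patients per cohort give at least an 80% chance that the true unacceptable rate is below 30%. With at most 1 event in 10:

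P(X ≤ 1 | n = 10, p = 0.30) = 0.7^10 + 10 × 0.3 × 0.7^9 = 0.0282 + 0.1211 = 0.1493.

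1 − 0.1493 = 85.1%, so the claim is met. Nothing in it depends on the item 2 limits.

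**2. The rules side by side.** Each state below either fails item 2 or triggers the study stop. Item 4 bars none of them if the disease has not relapsed or progressed.

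| State when infusion 2 or 3 is due | Section f) |
|---|---|
| Steroid-refractory GVHD or graft failure, any attribution | Study stops |
| Acute GVHD above grade I, IAC-related, CTCAE grade 3+, not recovered within 2 weeks | Barred |
| Severe chronic GVHD, IAC-related (assumed CTCAE grade 3+), not recovered within 2 weeks | Barred |
| Acute GVHD above grade I, IAC-related, below CTCAE grade 3, not refractory | Not clearly barred |
| Acute GVHD above grade I, judged unlikely related or unrelated, not refractory | Not clearly barred |
| Severe chronic GVHD, judged unlikely related or unrelated, not refractory | Not clearly barred |
| Donor CD3+ at or below 80%, short of graft failure | Not clearly barred |

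The fourth row depends on the two-week recovery sentence. If that sentence covers any IAC-related event, and not only grade 3+ events, it reaches this row too. The last three rows stay open on either reading. Item 2 uses CIBMTR staging and section f) uses CTCAE. The documents give no mapping between them, so the split at CTCAE grade 3 is taken case by case.

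**3. Ceiling on repeat infusions.** Up to 3 treatments means at most 3 − 1 = 2 repeats per patient. With k prophylactic patients among the 10 in Cohort 2, repeats are at most 2k: 0, 10 and 20 for k = 0, 5 and 10. The documents do not give k.

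**4. Age of a chimerism result, if none is taken after infusion 1.** The interval between infusions is 8 to 12 + 8 = 20 weeks. The result would be at least 8 to 20 weeks old at infusion 2. At infusion 3 it would be at least 2 × 8 = 16 to 2 × 20 = 40 weeks old, or up to 2 × 12 + 8 = 32 weeks if the delay may be used only once. This applies to chimerism alone, because clinical assessments are scheduled before each cycle and every 30 days.

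**The case against.** The case for leaving the text alone has real content.

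- **Item 2 may be a standing condition.** Its threshold sentence does not itself repeat the restriction to initial treatment, so a per-infusion reading is available. It is not stated, and neither item 4 nor the schedule repeats it. If it was intended, the fix only writes it down.
- **Clinical discretion.** Item 4 permits re-treatment and does not oblige it. Patients "receive standard treatment per Blood & Marrow Transplant Program Policies", and item 8 adds: "Management of cytopenias, infections, and other complications will conform to standard procedures at the discretion of the physician". A patient whose condition worsens is to be removed, each patient is reviewed weekly at two meetings, and the safety board looks at the data after the first 2-3 patients. All this allows an infusion to be withheld, but none of it sets a threshold. The sponsor wrote explicit limits for infusion 1 despite the same discretion. Removal from the study is also a different act from holding one infusion.
- **Attribution.** Possible relatedness counts as related, and GVHD is a listed anticipated toxicity, so much new GVHD after IAC would fall under the AE rule. This stands. The attribution gap is limited to GVHD judged unlikely related or unrelated.
- **Irradiation.** The background section says that irradiation ruled out engraftment and GVHD in the earlier study. The present protocol still lists GVHD and graft rejection as risks for allogeneic recipients.

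A reader might also infer that GVHD status is stale by infusion 2 or 3. The scheduled pre-cycle and 30-day assessments do not support that. For GVHD, what is missing is a written threshold, not current information.

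**Conclusion.** The point holds for prophylactic Cohort 2 patients. As written, the protocol does not clearly bar re-infusion in three states that would fail item 2 at the first infusion:

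- (a) acute GVHD above grade I, steroid-responsive or not yet refractory, that is below CTCAE grade 3 or judged unlikely related or unrelated to IAC;
- (b) severe chronic GVHD so judged and not steroid-refractory;
- (c) donor CD3+ at or below 80% short of graft failure.

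It is worth fixing as a cheap improvement, with moderate confidence. The ceiling is two repeat infusions per patient. It counts infusions given under the rule, not unsafe ones. No event rate can be derived, and the sample size justification is unaffected.

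Three stronger readings are not supported:

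- That nothing protects later infusions unless the event is attributed to IAC. The study stop for refractory GVHD or graft failure has no attribution condition.
- That moderate GVHD in general is the gap. Item 2 allows non-severe chronic GVHD even at infusion 1, and the clearest case is grade II acute GVHD.
- That relapsed Cohort 2 patients are included. Item 3 sets them no GVHD or chimerism condition to carry forward.

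The conclusion assumes that program policies, which are not in the documents, supply no binding threshold. If they do, citing them in item 4 would be enough.

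**What to change.** Add to item 4, for prophylactic Cohort 2 patients:

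- The item 2 GVHD condition, by CIBMTR staging, must be met at the existing pre-cycle assessment before each infusion.
- If the latest available donor CD3+ result since the previous infusion is 80% or below, the infusion is withheld until a result above 80% is documented.
- An infusion may be held for either reason within the 8-week delay already allowed. If the condition is still unmet when that delay ends, the infusion is omitted.
- The AE rule in section f) is unchanged. For example, IAC-related CTCAE grade 3 GVHD that resolves at week 6 stays excluded by the two-week rule. GVHD judged unrelated that resolves at week 6 may be followed by an infusion within the delay.

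Add a matching footnote to the pre-cycle column. At each infusion, record the GVHD stage and the latest chimerism value with its date.

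The GVHD condition closes states (a) and (b) on either reading of the two-week sentence. State (c) is closed only where a later chimerism result exists, since no new test is required.

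The cost is a few sentences, one footnote and two data items, with no new visit. The downside is that some infusions will be delayed or omitted. The background section reports that tumor responses came only after the second or third infusion, so this could cost some activity.
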